#### **4.5.3.7 Due to the small number of patients no analysis will be done for Part A.CYP2C19 Status on PK Parameters**

To assess CYP2C19 status on PK parameters, genotyping of CYP2C19 will be performed.

A mandatory whole blood sample will be taken for DNA extraction from every participant. The DNA may be used for the analysis of genetic variants of cytochrome P450, such as CYP2C19, that might affect the metabolism, PK, pharmacodynamics, or safety of RO6889450.

It has been suggested that genetic variation of CYP2C19 associated with decreased CYP2C19 enzyme activity might be related to an altered PK response to the study treatment. Therefore, to assess the effect of genetic variation of CYP2C19 on PK responses to RO6889450 the genotyping for CYP2C19 will be performed. Genotyping of CYP2C19 would allow for assay of the alleles frequencies. The different alleles of CYP2C19 that make up a genotype of a participant would indicate poor or enhanced metabolizer status.

Due to the small number of patients no analysis will be done for Part A.

#### **4.5.4 Other Efficacy Analyses**

##### **4.5.4.1 Sleep, Mood, Well-Being and Cognitive Functioning**

Sleep, mood, cognition and treatment expectation questions will be presented on the AiCure app at selected time points between Day 1 and Day 112 that will appear as random to the participant. Likert scales assessing sleep quality, mood / well-being, and cognitive functioning will be administered via the smartphone (see [Appendix 9](#)). Participant will be instructed to fill in the Likert scales (made of six smiley icons) at defined time points during the trial. In addition, participants will be asked to answer the following question at the end of the study: "Do you think you were taking placebo or drug?".

The Likert scale is a 6-point scale rating values range from 0 to 5. The higher the values, the better is the subjective well-being and cognitive functioning. Hence positive values for change from baseline indicate improvement.

The Likert scale data will be aggregated in 3-weeks intervals, i.e. ≤ Day 1, (Day 1, Day 21], (Day 21, Day 42], (Day 42, Day 63], (Day 63, Day 84], (Day 84, Day 112]. If more than one value is in an interval, the last value in the interval will be used.

The Likert scale scores and change from baseline will be summarized by time interval.

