## Appendix 9 Assessment of Sleep, Mood, Well-being and Cognitive Functioning, and Assumed Treatment Assignment

### Sleep (treatment period)

“How did you sleep last night?”

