### Mood & Well-being (treatment period)

“How are you feeling today?”

“How is your energy level today?”

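### When a participant gives several app answers in an interval, SAP 4.5.4.1 summarises only the last, so for items about last night or today one day stands for 20 to 28 days

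*SAP*

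**What the plan says.** SAP 4.5.4.1 presents the app questions "at selected time points between Day 1 and Day 112 that will appear as random to the participant". It says of the answers: "The Likert scale is a 6-point scale rating values range from 0 to 5", with higher values better. On data reduction it says "The Likert scale data will be aggregated in 3-weeks intervals", lists the bounds (up to Day 1, then upper limits at Days 21, 42, 63, 84 and 112), and adds: "If more than one value is in an interval, the last value in the interval will be used". The output is then defined: "The Likert scale scores and change from baseline will be summarized by time interval".

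The recall period is in SAP Appendix 9. The sleep item asks "How did you sleep last night"; the mood and energy items ask "How are you feeling today" and "How is your energy level today"; the cognition item also refers to the current day. Protocol 8.1.3.2 fixes only that the scales are given at pre-specified times that look random to the participant. It sets no rule for combining answers.

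**The concern.** The section speaks of aggregating, but the rule selects a single answer. Repeated prompting is useful for items with a one-day recall because it averages out day-to-day variation, and keeping only the last answer gives up that benefit. The retained day also differs between participants, since it depends on which prompt each person answered last.

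The SAP treats other repeated measures differently. For the effort-choice task (4.5.3.1) and the learning phase of the reinforcement learning task (4.5.3.2), a percentage over repeated trials is first derived within each participant and then summarised by arm. No reason is given for handling the app items otherwise.

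At stake is the readability of one descriptive table. SAP 1 reports 27 randomized participants in Part A, over two arms, so avoidable noise in each participant's score will show in the arm summaries.

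**Working it through.** The plan states no figure for this rule, so there is none to reproduce. Two quantities can be worked out.

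**Days represented by one answer.** From the bounds in SAP 4.5.4.1, each interval open on the left:

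- (Day 1, Day 21]: 21 − 1 = 20 days; one day is 1/20 = 5.0%.
- (Day 21, Day 42], (Day 42, Day 63] and (Day 63, Day 84]: 21 days each; 1/21 = 4.8%.
- (Day 84, Day 112]: 112 − 84 = 28 days; 1/28 = 3.6%. This interval covers four weeks, although the text calls all of them three-week intervals.

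With k answers in an interval, the share left out of the summary is 1 − 1/k: none at k = 1, 50% at k = 2, 67% at k = 3, 89% at k = 9.

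**Precision of the mean against the last answer.** Let each answer have variance σ², and let any two answers from one participant in one interval have correlation ρ. The last answer has variance σ². The mean of k answers has variance σ²(1 + (k − 1)ρ)/k. The ratio is therefore (1 + (k − 1)ρ)/k.

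Neither k nor ρ is in the documents, so both are assumptions:

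| k | ρ | Variance ratio | SD ratio |
|---|---|---|---|
| 1 | any | 1.00 | 1.00 |
| 2 | 0.3 | 1.3/2 = 0.65 | 0.81 |
| 2 | 0.7 | 1.7/2 = 0.85 | 0.92 |
| 3 | 0.5 | 2.0/3 = 0.67 | 0.82 |
| 3 | 0.7 | 2.4/3 = 0.80 | 0.89 |
| 5 | 0.5 | 3.0/5 = 0.60 | 0.77 |
| 9 | 0.3 | 3.4/9 = 0.38 | 0.61 |
| 9 | 0.7 | 6.6/9 = 0.73 | 0.86 |

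Over k = 2 to 9 and ρ = 0.3 to 0.7 the variance ratio runs from 0.38 to 0.85, and the SD ratio from 0.61 to 0.92. Under this model the ratio is below 1 whenever k exceeds 1 and ρ is below 1, so the mean cannot lose precision.

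**The case against.** Several points against the concern have force.

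- **The rule may rarely apply.** It operates only when an interval holds more than one answer, and the number of prompts is not stated. If each interval has one prompt, the two rules agree. This stands, and makes the point conditional.
- **The last value is a defensible choice.** It lies nearest to the end of the interval, which suits an effect that builds over 12 weeks. A mean blends earlier and later days, and gives scores of unequal precision when answer counts differ. It would also dilute a late deterioration that a reader may want to see. This stands as a real, modest downside.
- **The size is assumed.** The calculation takes equal variances, a common correlation and no trend within the interval. That also stands, and is why a range is given.
- **Little hangs on the table.** The scales are absent from the SAP's objectives and endpoints table and sit under other efficacy analyses. SAP 4.5 plans no test for Part A efficacy, and Part B has its own analysis document.

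Two stronger readings are tempting but not supported. A reader might infer that the earlier answers are lost. SAP 4 provides for Part A data to be listed as well as summarised, so they leave the summary, not the record. A reader might also infer, from the treatment-period labels in Appendix 9, that no baseline answers exist and change from baseline fails. The questions run from Day 1, which falls in the interval up to Day 1, and Protocol 8.11.1 starts the treatment period with the eligibility-confirmation call at baseline. The schedule tables, in the form available, do not show that baseline answers are absent. In any case the interval scores are already to be summarised beside the change.

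**Conclusion.** The point holds in a limited form. Where a participant has several answers in an interval, the rule represents 20 to 28 days by one day and leaves the rest out of the summary. Using the mean would bring the variance of a participant's interval score to roughly 0.38 to 0.85 of its value under the last-answer rule. That range assumes 2 to 9 answers, correlation 0.3 to 0.7, equal variances and exchangeable answers. Where there is one answer, nothing changes.

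The documents do not show how often several answers occur, and give no ground for saying that the rule favours either arm. This is an optional improvement, not an error that affects a conclusion of the trial.

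**What to change.** Replace the last-value sentence in SAP 4.5.4.1 with wording to this effect: *for each item, a participant's score for an interval is the mean of all answers in that interval, and the number of contributing answers is shown.* The last value can stay as a sensitivity summary for readers interested in the end of the interval.

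Two small clarifications belong with it. Say whether the interval up to Day 1 also takes the mean or keeps the last value, which is how SAP 4.4 defines baseline in general. Describe (Day 84, Day 112] as a four-week interval.

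The cost is a sentence or two in the SAP and one more column in the table. No new data are needed. The price in interpretation is that the score describes the whole interval and says less about its end.

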## PHARMACOKINETIC AND PHARMACODYNAMIC ANALYSES

To evaluate the PK of RO6889450 and RO6889450-derived metabolite(s), concentration per time point,  $AUC_{ss}$  and  $C_{max}$  of RO6889450 and RO6889450-derived metabolite(s), and other PK parameters as appropriate will be collected.

Blood samples for measurement of plasma concentrations of RO6889450 and derived metabolite(s) will be collected at Day 7, Day 14, Day 42, Day 84/EOT, Day 112 (FU).

Plasma concentrations will be summarized descriptively by treatment arm per time points: the number of non-missing values, arithmetic mean, geometric mean, coefficient of variation, standard deviation, minimum and maximum will be reported.

$AUC_{ss}$ ,  $C_{max}$  of RO6889450 and, if feasible, of RO6889450-derived metabolite(s) and other PK parameter as appropriate will be analyzed.

Population PK analyses will only be performed after Part B is completed.

Pharmacodynamic effects will not be assessed in this study.

## 4.6 SAFETY ANALYSES

The safety analysis will be conducted to compare the safety and the tolerability of 12 weeks of treatment with RO6889450 as monotherapy (Part A) with placebo. Safety assessments will consist of monitoring and recording AEs, including SAEs, measurement of protocol-specified safety laboratory assessments, measurement of protocol-specified vital signs, ECGs, and other protocol-specified tests that are deemed critical to the safety evaluation of the study.

All safety analyses will be based on the safety analysis population grouped according to the treatment assigned at randomization.

### 4.6.1 Exposure of Study Medication

The following extent of exposure to randomized study medication will be summarized by randomized treatment arm:

- Duration of treatment (weeks), which will be calculated from the first day of randomized double-blind study medication intake as recorded with AICURE to the last day of randomized double-blind study treatment intake as recorded with AICURE, i.e. last dosing date minus first dosing date plus 1 day (divided by 7 to get weeks).
- Number of doses over the whole double-blind treatment period derived from the number of days at which randomized double-blind treatment was taken as recorded with AICURE.
- Total cumulative dose (mg) over the whole double-blind treatment period as

recorded with AICURE.

- Extent of compliance with randomized double-blind treatment (%). Treatment compliance for each participant will be calculated as actually taken dose divided by planned dose of double-blind treatment. The actually taken dose will be the total cumulative dose. The planned dose is the cumulative planned dose over 84 days, i.e., [REDACTED] x84 days.

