- 10 One additional sample should be taken two hours (± 0.5) post-dose.
- 11 Samples can be taken at any time between baseline and follow-up.
- 12 The Study Phone Usage Tracker will be used only with screened patients who have suitable smartphones and agree to the assessment.
- After informed consent, but prior to initiation of study drug, only SAEs caused by a protocol-mandated intervention will be collected. After initiation of study drug, all adverse events, regardless of relationship to study drug, will be reported until 28 days after the last dose of study drug.
- 14 The placebo compliance period will start with a visit reviewing instructions with the patient.
- 15 Study drug is three capsules administered once daily, preferably in the morning. The last dose is given at the Day 84/EOT visit.
- 16 Sleep, mood, cognition and treatment expectation questions will be presented on the AiCure app at select time points that will appear as random to the participant.
- 17 The exploratory endpoints Brief Assessment of Cognition in Schizophrenia (BACS) (digital version), Wechsler Abbreviated Scale of Intelligence Second Edition (WASI-II), Wide Range Achievement Test (WRAT-4) and Virtual Reality Functional Capacity Assessment Tool (VRFCAT) are not available as validated Spanish translation. Therefore, sites will not be required to administer these tests to Spanish only speaking patients. If validated versions become available, they may be used.

Table 2 Schedule of Activities for Part B of the Study

Period	Scre	ening																
		Placebo Compliance ¹ 4							Treatment								Follow Up Vis	its
Week	Week -5 to -2	Week -1	1	ı	2	3	4	5	6	7	8	9	10	11	12	13	14	15
Day	Day -35 to Day -8	Day -7	Baseline ¹ / Day 1	Day 7	Day 14	Day 21	Day 28	Day 35	Day 42 ¹	Day 49	Day 56	Day 63	Day 70	Day 77	Day 84/ EOT ^{1, 2}	Day 91	Day 98	Day 112 ²
Visit Window (days) ²⁰		±1	-1	Ħ	±1	±1	±2	±2	±2	±2	±2	±2	±2	±2	±2	±2	±2	±4
On-site visit	Х	х	х	Х	х		х		Х		Х				Х			Х
Phone Call						х		х		х		х	х	х		х	х	
Informed Consent	Х																	
Inclusion/exclusion criteria	Х		X 3															
Eligibility Checklist Form Submission	•																	
Randomization			х															
Demography	Х																	
Medical History	Х																	
Physical Examination ^{4 16}	X ²³	х	X ²³	Х	Х		Х		Х		X ²³				X ²³			X ²³
ECG-12 lead ^{5 16}	Х		Х	Х	Х		Х		Х		Х				Х			Х
Meal time ¹⁶	х		х		Х						Х				Х			х
Vital Signs ¹⁶	Х		х	Х	х		х		Х		Х				Х			Х

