6.1 TREATMENTS ADMINISTERED

Table 5 summarizes the treatments administered. Of note, the daily dose of study drug has been increased in Part B of the study (*from* protocol Version 5: RO6889450, or placebo).

Table 5 Summary of Treatments Administered

Study Part A				
Study Drug Name:		RO6889450 (IMP)	RO6889450 (placebo; IMP)	
Dosage Formulation:		Hard capsules	Hard capsules	
Strength:			N/A	
Route of Administration:		Oral	Oral	
Dosing Instructions:		3 capsules QD	3 capsules QD	
Daily Dose of RO6889450			NA	
Packaging and Labeling ^a		HDPE bottle	HDPE bottle	
Storage Conditions		Do not store above 30°C, protect from light, keep container tightly closed.	Do not store above 30°C, protect from light, keep container tightly closed.	
	Study Part B (prior to	Protocol Version 5)		
Study Drug Name:	RO6889450 (IMP)	RO6889450 (IMP)	RO6889450 (placebo; IMP)	
Dosage Formulation:	Hard capsules	Hard capsules	Hard capsules	
Strength:			N/A	
Route of Administration:	Oral	Oral	Oral	
Dosing Instructions:	3 capsules QD	3 capsules QD	3 capsules QD	
Daily Dose of RO6889450			NA	
Packaging and Labelinga	HDPE bottle	HDPE bottle	HDPE bottle	
Storage Conditions	Do not store above 30°C, protect from light, keep container tightly closed.	Do not store above 30°C, protect from light, keep container tightly closed.	Do not store above 30°C, protect from light, keep container tightly closed.	

Table 4 Summary of Treatments Administered (cont.)

Study Part B (from Protocol Version 5)				
Study Drug Name:	RO6889450 (IMP)	RO6889450 (placebo; IMP)		
Dosage Formulation:	Hard capsules	Hard capsules		
Strength:		N/A		
Route of Administration:	Oral	Oral		
Dosing Instructions:	Patients will take 3 capsules from each of two bottles (total 6 capsules) once daily, preferably in the morning, with or without food.			
arm	3 capsules and	3 capsules placebo QD		
arm	6 capsules QD (three from each of two bottles)	N/A		
Placebo arm	N/A	6 capsules QD (three from each of two bottles)		
Daily Dose of RO6889450		NA		
Packaging and Labeling ^a				
arm	1 HDPE bottle	1 HDPE bottle		
arm Placebo arm	2 HDPE bottles N/A	N/A 2 HDPE bottles		
Storage Conditions	Do not store above	Do not store above		
Storage Conditions	30°C, protect from light, keep container tightly closed.	30°C, protect from light, keep container tightly closed.		

Abbreviations: HDPE = high density polyethylene; IMP = investigational medicinal product; N/A = not applicable; QD = once a day

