6.5.1 Rescue Medicine During Part A

If early signs of relapse requiring treatment are noticed/recorded by the Investigator, an antipsychotic should be prescribed and the participant will be immediately withdrawn from the study drug. Investigators should make reasonable effort to complete a final assessment including efficacy endpoints before starting antipsychotic medication.

6.5.2 Permitted Therapy

Concomitant therapy includes any medication, e.g., prescription drugs, OTC drugs, approved dietary and herbal supplements, nutritional supplements and any non-medication interventions (e.g., individual psychotherapy, cognitive behavioral therapy, smoking cessation therapy, and rehabilitative therapy) used by a participant from 28 days prior to screening until the follow-up visits. All concomitant medications should be reported to the Investigator and recorded in the eCRF.

All therapy and/or medication administered to manage adverse events should be recorded on the AE eCRF. For further information regarding the management of specific AE, please see Appendix 2.

The use of stable, scheduled doses of benzodiazepines is permitted. The use of stable, scheduled doses of non-benzodiazepine hypnotics is permitted.

If deemed necessary by the Investigator to treat occasional anxiety, agitation, or sleep problems, lorazepam, alprazolam, or oxazepam are allowed as needed ([PRN], up to a maximum daily dose of lorazepam 6 mg, alprazolam 3 mg, or oxazepam 90 mg). If PRN treatment of more than five consecutive days is necessary, this should be discussed with the Medical Monitor. PRN doses of benzodiazepines should not be administered within 12 hours of a clinic visit.

Non-prohibited medications used for the treatment of stable medical conditions other than schizophrenia (e.g., hypertension, diabetes, oral contraceptives, hormone-replacement therapy) are allowed during the study, provided that they have been stable for 28 days prior to screening and are intended to remain stable throughout the study up to the follow-up visits.

Participants in Part B of the study have to be on stable treatment (i.e., no medication changes or significant dose adjustments) with D2/5HT2A antagonists or D2 partial agonist for a minimum of six months prior to screening. In cases where change in medication is not associated with the participant's psychiatric stability, treatment changes can be accepted up to three months prior to screening.

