### Length of Study

**Part A:** The total duration will be approximately 147 days (from screening through study completion) for each enrolled participant as follows:

- Screening up to 35 days (including the placebo compliance and a 7-day washout period)
- Treatment period: 84 days (12 weeks)
- Follow up: 28 days

[figure not shown]
**Part B:** The total duration will be up to approximately 147 days (from screening through study completion) for each enrolled participant as follows:

- Screening: up to 35 days (including the placebo compliance period)
- Treatment period: 84 days (12 weeks)
- Follow up: 28 days

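### Part A compliance is computed against 84 planned days for everyone, so early discontinuation lowers the percentage even when no dose was missed

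*SAP*

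**What the plan says.** SAP 4.6.1 (Exposure of Study Medication) lists four summaries by randomized arm: duration of treatment, number of doses, cumulative dose and compliance. The compliance rule is: "Treatment compliance for each participant will be calculated as actually taken dose divided by planned dose of double-blind treatment". The numerator is fixed by "The actually taken dose will be the total cumulative dose", which the same list introduces as "Total cumulative dose (mg) over the whole double-blind treatment period as" recorded by the adherence app. The denominator is fixed by "The planned dose is the cumulative planned dose over 84 days", followed by a daily amount that is redacted in the public copy, multiplied by 84. No sentence deals with participants who stop early.

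Those participants are in the table. SAP 4.1 (Table 2) makes the safety population identical to the modified ITT population, which explicitly keeps premature withdrawals. SAP 4.7 keeps people who took study medication only in part.

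Early stopping is part of the Part A design. For early signs of relapse requiring treatment, Protocol 6.5.1 says that "an antipsychotic should be prescribed and the participant will be immediately withdrawn from the study drug". SAP 2.3 planned for 20% of randomized participants not completing 12 weeks.

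**The concern.** A figure labelled compliance will be read as how faithfully participants took the drug while they were meant to take it. With a fixed 84-day denominator it also carries how long they stayed on treatment, and the reader of the percentage cannot separate the two. Time on treatment is already reported as duration, and with once-daily dosing the percentage is close to a rescaling of the dose count in the same list. So no row of the exposure table directly reports adherence on treatment, although the protocol runs a dedicated monitoring platform to verify it (Protocol 6.4 and 6.4.1).

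The by-arm comparison is where this could mislead. SAP 2.2 (Table 1) has an exploratory Part A objective on the rate and timing of relapse and withdrawal by arm, so the plan itself allows that withdrawal may differ. If it does, the compliance row would show a difference between arms even if every participant took every dose due.

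**Working it through.** **Inputs**
- Planned course: 12 weeks, 84 days (SAP, Length of Study). Check: 12 × 7 = 84, which reproduces the denominator in SAP 4.6.1.
- Dosing: "Study drug is three capsules administered once daily, preferably in the morning" (Protocol 1.3, Part A footnotes), with no dosage modification allowed (Protocol 6.6).
- Participants randomized in Part A: 27 (SAP 1). Planned non-completion: 20% (SAP 2.3).
- Stop days and arm-level dropout counts are not in the documents. The values below are assumptions.

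**What the formula reduces to.** Let d be the redacted daily dose. With full daily doses in the active arm, compliance = (d × doses taken) / (d × 84) = doses taken / 84. The redacted amount cancels. If P is the number of dosing days planned up to the stop, then

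doses taken / 84 = (doses taken / P) × (P / 84),

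that is, adherence on treatment multiplied by the fraction of the course reached.

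**Single participant, every dose taken until the stop**

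| Last dosing day | SAP 4.6.1 | On-treatment denominator |
|---|---|---|
| 14 | 14/84 = 16.7% | 14/14 = 100% |
| 28 | 28/84 = 33.3% | 28/28 = 100% |
| 42 | 42/84 = 50.0% | 42/42 = 100% |
| 56 | 56/84 = 66.7% | 56/56 = 100% |
| 70 | 70/84 = 83.3% | 70/70 = 100% |

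The Day 42 stopper has the same 50.0% as a completer who took every second dose (42/84).

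**Arm mean, everyone fully adherent.** With a fraction f stopping at day s, mean = (1 − f) + f × s/84.
- f = 20% (the planning figure), s = 14: 0.80 + 0.20 × 14/84 = 83.3%.
- f = 20%, s = 56: 0.80 + 0.20 × 56/84 = 93.3%.
- f = 40% (assumed), s = 14 to 56: 66.7% to 86.7%.

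**Difference between arms, everyone fully adherent.** Assume 13 per arm and all stops at Day 28.
- 4 stoppers: (9 + 4 × 28/84)/13 = 79.5%.
- 1 stopper: (12 + 1 × 28/84)/13 = 94.9%.
- Apparent difference: 15.4 percentage points, all of it from dropout. One such stopper moves an arm mean by (1 − 28/84)/13 = 5.1 points.

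**The case against.** The strongest reply is that this is a matter of definition. The item sits under extent of exposure, 84 days is the planned course, and the share of that course received is a coherent quantity. The material for reading it correctly is also planned: duration and number of doses in the same section, discontinuations with reasons in SAP 4.2.1, relapse and withdrawal by arm in SAP 2.2, and time to exacerbation in SAP 4.6.2. Differential withdrawal would be visible elsewhere. This stands as a limit on the consequences. It does not rescue the label: share of planned course received is not compliance, and the table would carry it under that name.

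Three stronger readings are tempting, and the documents do not support them.
- A reader might infer that early stoppers are classed as poor compliers. Part A sets no cut-off and SAP 4.1 defines no per-protocol set. The only numeric limits, below 80% or above 120%, belong to the Part B placebo run-in (Protocol 1.3, Table 2 footnotes). Participants receive a low percentage; nobody is flagged or excluded.
- A reader might infer that placebo compliance is undefined (0/0), because the numerator is in mg and the Part A placebo entry for "Daily Dose of RO6889450" in Protocol 6.1 is NA. The daily factor in the denominator is redacted, so a nominal or capsule-based convention for placebo cannot be ruled out. The visible text states no placebo rule; more cannot be said.
- A reader might infer that low compliance will be used to explain away a weak effect. Nothing in the documents plans that.

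**Conclusion.** The point holds for the denominator. As written, the Part A compliance percentage mixes adherence with time on treatment. It understates adherence for anyone who stops early, down to 16.7% for a full adherer stopping at Day 14, and can produce a difference between arms from dropout alone. The single-participant figures follow directly from the stated rule. The arm-level figures depend on assumed stop days and dropout splits and show scale only; the documents give no dropout by arm.

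The reach is small. Part A ended with 27 randomized, SAP 4 and 4.5 make its efficacy analysis descriptive with no hypothesis test, and no analysis set depends on compliance. One exposure summary is affected and no efficacy or safety result changes. It is worth correcting because a stated rule gives a misleading number and the correction is nearly free.

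**What to change.** In SAP 4.6.1, define compliance in both arms as dosing days (or capsules) taken, divided by dosing days (or capsules) planned from first dose to the last planned dosing day before discontinuation, at most the planned treatment period. Running the denominator to the last planned day, and not to the last dose actually taken, keeps doses missed just before discontinuation in the count.

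Keep duration of treatment as the measure of persistence. If doses taken over 84 days is still wanted, report it separately as the proportion of the planned course received.

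Counting days or capsules also gives the same measure in both arms, since each Part A arm takes three capsules once daily (Protocol 6.1), and removes any reliance on a mg dose for placebo.

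The cost is about one sentence in the SAP and a small programming change. The intake data are already in the adherence platform. Protocol 7.1.2 has the reason for stopping study drug recorded in the eCRF; I assume that the date is recorded with it.
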